### 5.1.3 Audio-recording of interviews

A sub-set of the participants in the COVID-19 Rapid Response sub-study will participate in an audio-recorded semi-structured, one-on-one telephone interview with a study team member. Interview audio recordings will be transcribed by ADA Transcription (<http://www.adatranscription.com/>). Audio recordings will be de-identified and sent via their secure server, and subsequent transcripts will be saved on a secure server accessed only by members of the study team.

Interviews from Phase 2 of the Trauma-Informed Co-parenting Sub-study will be recorded, transcribed (by ADA Transcription (<http://www.adatranscription.com/>) and/or a member of the research team), de-identified, and entered into NVivo 12.0 for coding and analysis. Recordings will be de-identified and sent via their secure server, and subsequent transcripts will be saved on a secure server accessed only by members of the study team.

## 5.2 Safety Evaluation

Subject safety will be monitored by adverse events reporting. As this study is not greater than minimal risk serious adverse events are not anticipated.

# 6 STATISTICAL CONSIDERATIONS

## 6.1 Primary Endpoint

In order to determine the effectiveness of the Opening Doors to Early Intervention Program on child developmental status, our primary outcome for this aim is the Bayley-III cognitive subscale measured at 12 months follow-up.

## 6.2 Secondary Endpoints

Secondary outcomes include the Bayley-III language, motor, and socioemotional subscales and the binary outcomes of whether patients complete EI referrals and services at 12 months.

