The study research materials will consist of parent- and observer-reported instruments and EI data. Following written informed consent (which is either completed in person or remotely with the electronic REDCap e-consent process), participant caregivers will complete a baseline visit. Measures of demographic characteristics (child age, sex, race/ethnicity, family income, maternal education level, spoken language, and family structure) (Appendix 2), parental health literacy (SAHL) (Appendix 3), and the home learning environment (StimQ) (Appendix 4) will be collected at this visit. Due to the interactive nature of the SAHL measure, in the event that the baseline visit is conducted remotely, the participant will have the option of either completing the measure of parental health literacy (SAHL) remotely by utilizing a video conferencing application or completing the SAHL in-person at a later date. If a visit is conducted using a video conferencing application, we will try to use a HIPAA-compliant application licensed by CHOP (i.e., Skype, Bluejeans or WebEx). Measures of parent engagement and EI referral and service use will be collected at follow-up visits at 3, 6, 9, and 12 months. These visits will be conducted in-person, by telephone, or by email at the preference of the parent. Parents will be asked at study visits to complete the EI Engagement questionnaire, which was adapted from the CECPS and generated during a prior study (IRB 18-014884), and measures of completion of EI referrals (intake, registration, assignment of service coordinator, home visit, and MDE), eligibility for and initiation of EI services (IFSP), EI services use if eligible (number of EI service visits and whether services were completed or terminated), and use of other services (transfer to Preschool EI services, childcare or preschool enrollment). We will corroborate parent-reported visits with EI staff. Participants will also complete the Philadelphia Expanded ACE measure at one time-point throughout the study. This time-point will typically be the 3-month survey, however the measure may be administered during either the 6- 9- or 12-month follow-up survey time-points in the event that the survey is not completed during the 3-month time-point. The ACEs survey assesses for adverse events in that have already occurred in the past (i.e., childhood adverse experiences),

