Measures of engagement will be collected at baseline and at follow-up visits every 3months, while EI referral and service use will be collected at follow-up visits every 3 months. In addition, public policy changes that may impact access to services (e.g. changes in EI funding or eligibility) will be queried of EI staff throughout the study period. The visits will be conducted by research staff blinded to randomization assignment by telephone or email at the discretion of the parent. The Client Engagement in Child Protective Services (CECPS, Appendix 1) is a validated 14-item measure of parent engagement in child welfare services and contains 4 subscales: receptivity, working relationship, buy-in, and mistrust Reliability was good ( $\alpha=0.95$  for the total score and  $\alpha=0.81-0.91$  for subscale scores), and correlation with measures of global engagement and helping relationships and personal support was moderate to strong ( $r=0.36$  to  $0.78$ ). Following discussions with the author of the CECPS (personal communication with [name]), the CECPS will be adapted for an EI population by conducting semi-structured interviews and cognitive testing with a separate group of parents previously referred to EI from one of the urban practices to identify new items and refine the wording on existing items. The adaption of the CECPS measure will be carried out as part of a separate study (IRB 18-014884). We have previously adapted an engagement measure for ADHD using a similar process (See Appendix). Parents will be asked at study visits to complete the adapted CECPS, which we are referring to as the EI Engagement questionnaire, and measures of completion of EI referrals (intake, registration, assignment of service coordinator, home visit, and MDE), eligibility for and initiation of EI services (IFSP), EI services use if eligible (number of EI service visits and duration of EI service visits), and use of other services (transfer to Preschool EI services, childcare or preschool enrollment). We will corroborate parent-reported visits with EI staff.

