ODEI Study Statistical Analyses Plan

Title: The Opening Doors to Early Intervention Study (ODEI)

NCT Number: NCT03625115

Document Date: July 3rd, 2024

ODEI Study Statistical Analyses Plan

Aim 1: To test the effectiveness of the Opening Doors to Early Intervention Program on EI service use and child developmental status among poor minority children residing in an urban community.

- a. *Hypothesis 1a:* A greater proportion of children who are randomized to the intervention will complete EI referrals than children in the control condition at 12 months.

Analysis: Chi square analysis on the difference in completion of MDE by study arm and logistic regression on the difference in MDE completion by arm, controlling for sex, age, and primary care site.

- b. *Hypothesis 1b:* Among children eligible for EI services, children randomized to the intervention will initiate EI services at a greater rate & receiving a longer duration of EI services than children in the control condition.

Analysis: Chi square test on the difference in EI service initiation by arm and logistic regression, controlled for sex, age, and primary care site. Survival analysis with a Kaplan-Meier curve of EI duration of services by arm.

- c. *Hypothesis 1c:* As a result, children who are randomized to the intervention will have more favorable developmental outcomes than children in the control condition at 12 months.

Analysis: Logistic regressions to determine the difference in cognitive and language BSID III scores by arm, controlling for sex, age, and primary care site.

Variable Definitions:

- Completion of EI Referrals: Completion of Multidisciplinary Evaluation (MDE)
- Initiating EI services: Date of first early intervention service
- Duration of EI services: The time between the EI service initiation and discharge from early intervention OR 12 months from randomization (if discharge date is unavailable)
- Developmental outcomes: Language and cognitive composite scores from BSID III assessment.

Aim 2: To assess whether parent engagement mediates the effects of the Opening Doors to Early Intervention Program.

- a. *Hypothesis 2a:* Parent engagement will mediate the association between program participation and completion of EI referrals and participation in EI services (duration).

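### Completion of EI services is a named but undefined binary secondary outcome; the SAP replaces it, without saying so, with initiation among eligible children only

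*Protocol*

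**What the plan says.** **Outcome.** Protocol 6.2, repeated in 6.4.2.1, lists "the binary outcomes of whether patients complete EI referrals and services at 12 months" among the secondary outcomes. No section says what counts as having completed services.

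**Data items.** Protocol 3.1.1 collects, for eligible children, "number of EI service visits and whether services were completed or terminated". Section 5.1.2.1 describes the same item as "EI services use if eligible (number of EI service visits and duration of EI service visits", with no completed or terminated status. Section 3.2 again refers to measures of service completion. Both 3.1.1 and 5.1.2.1 list initiation as a separate item with the IFSP as its marker: "eligibility for and initiation of EI services (IFSP".

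**SAP.** Hypothesis 1a covers referral completion, defined as completion of the MDE. Hypothesis 1b reads "Among children eligible for EI services, children randomized to the intervention will initiate EI services at a greater rate". Its analysis is a "Chi square test on the difference in EI service initiation by arm and logistic regression", plus a Kaplan-Meier curve for duration of services. The variable definition is "Initiating EI services: Date of first early intervention service". Duration ends at discharge or, if no discharge date is available, at 12 months from randomisation.

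**Denominator.** Protocol 6.4.2.1 restricts only the dosage analysis (duration and number of visits) to eligible children. It places no such limit on the binary outcomes.

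**The concern.** Starting services and completing them are different events. A child still in service at month 12, or one who started and then dropped out, counts as a success under the SAP and is not a completer under the protocol's wording. If the SAP is followed, a named secondary outcome goes unreported and another takes its place without a declared change. That invites a charge of outcome switching, on a result that is half of Aim 1.

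The denominator also changes. Eligibility is listed after the referral steps, which end in the MDE, and Hypothesis 1a expects navigation to raise MDE completion. The eligible children in the two arms are therefore reached through a process that the intervention alters, and comparing them no longer has the protection of randomisation.

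Finally, initiation has two markers, the IFSP and the first delivered service, so the rate depends on which field is extracted.

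**Working it through.** **1. The documents side by side**

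| Element | Protocol | SAP |
|---|---|---|
| Referral outcome | Completed; last listed step is the MDE | Completed = MDE (1a) |
| Binary service outcome | Completed at 12 months, undefined | Initiated (1b) |
| Marker of initiation | IFSP | Date of first service |
| Denominator, binary service outcome | No restriction stated | Eligible children |
| Window for service outcome | 12 months | Not stated for initiation |
| Completed versus terminated | Collected in 3.1.1, absent from 5.1.2.1 | Not used |

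The referral row agrees. Every service row differs or is incomplete.

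**2. Plan figures used.** Protocol 6.5 gives EI enrolment of 50% (control) and 80% (intervention), and about 130 and 170 children with complete follow-up. Its 3-point effect reproduces: (0.80 − 0.50) × 10 = 3. The stated 96% power is for the Bayley-III cognitive score; no power is given for a binary EI outcome. With 360 randomised 1:1 there are 180 per arm.

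**3. Power if the event is completion rather than initiation.** Assumptions: two-sided 0.05; enrolment stands for having started; the same fraction c of starters completes by month 12 in both arms; all children in the denominator. None of these is in the documents.

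Power = Φ[(d − 1.96·SE0)/SE1], with SE0 = √[p̄(1 − p̄)(1/n1 + 1/n2)] and SE1 = √[p1(1 − p1)/n1 + p2(1 − p2)/n2].

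Example, c = 20%, 130/170: rates are 0.10 and 0.16, and p̄ = (13 + 27.2)/300 = 0.134. SE0 = 0.0397 and SE1 = 0.0385. Power = Φ[(0.06 − 0.0778)/0.0385] = Φ(−0.46) = 0.32.

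| Event | Control v intervention | 130/170 | 180/180 |
|---|---|---|---|
| Initiated | 50% v 80% | >99.9% | >99.9% |
| Completed, c = 50% | 25% v 40% | 79% | 86% |
| Completed, c = 40% | 20% v 32% | 65% | 74% |
| Completed, c = 30% | 15% v 24% | 49% | 58% |
| Completed, c = 20% | 10% v 16% | 32% | 39% |

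**4. Marker of initiation.** Take 50% and 80% as IFSP rates. If a share g of IFSP families in both arms never receives a service (assumed 5% to 20%), the difference is 0.30 × (1 − g): 28.5 points at 5%, 24 at 20%. At 20% the rates are 40% and 64%, and power on 130/170 is still 98.7%. If the loss is 20% in controls and 5% with a navigator, the difference is 0.80 × 0.95 − 0.50 × 0.80 = 36 points. The marker shifts the estimate by several points but hardly affects power.

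**5. Denominator.** Write enrolment in each arm as the share found eligible times the share of eligible children who start. If navigation acts only on the first factor and the second is equal in both arms (an illustrative extreme), the eligible-only difference is 0 while the all-randomised difference is 80 − 50 = 30 points. The documents do not say how the gain divides between the two factors.

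**The case against.** The strongest replies are these.

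- **The secondary endpoint is not abandoned.** This stands in part. A reader might infer that the whole outcome goes unanalysed, but referral completion is tested under Hypothesis 1a with a consistent definition. Only the service half is lost.
- **The duration curve covers the end of services.** It does so only partly. Discharge does not separate completed from terminated, and the protocol treats duration as dosage, apart from the binary outcome.
- **The IFSP is not a rival definition of the endpoint.** This stands. Section 3.1.1 collects IFSP initiation and completed or terminated status as distinct items. The fault is a missing definition plus a substitution in the SAP.
- **The effect on counts is unknown.** This stands. One might infer that successes change several-fold, but no completion rate is given. If 20% to 50% of starters complete, completers are one fifth to one half of starters; a higher rate would shrink the gap.
- **Completion by month 12 might seem out of reach.** Protocol 3.4 does not show this: its remark about little time for completion explains why children over 30 months are excluded.
- **The power inputs fit loosely.** This stands. The 130/170 split comes from the Bayley calculation, and agency records could support up to 180/180. The 50% and 80% rates are for all children, so they are not the SAP's eligible-only comparison. Nor does the table show that an effect on uptake would go unseen, since referral completion and dosage remain planned analyses.
- **Ineligible children cannot receive services, so restricting is natural.** That is fair as a supportive analysis. As the only one, it conditions on a status observed after randomisation.

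**Conclusion.** The point holds as a documentation and analysis fault. The protocol's service-completion outcome is undefined, and the SAP replaces it undeclared with initiation, restricted to a subset identified after randomisation. Two smaller inconsistencies go with it: IFSP versus first service as the marker of initiation, and disagreement between 3.1.1 and 5.1.2.1 on whether completed or terminated status is collected.

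The documents do not determine the size. The completion power range of 32% to 86% rests on the assumed 20% to 50% completion, equal in both arms, and on enrolment standing for a start. It shows that the choice of event can matter; it does not predict what the trial will find. The primary outcome is unaffected, so this should be corrected but does not threaten the trial's main comparison.

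**What to change.** 1. **Settle the event.** Either add to the SAP a binary analysis of service completion at 12 months, with an explicit definition based on the completed or terminated item in Protocol 3.1.1 and with 5.1.2.1 brought into line; or formally declare that first EI service within 12 months of randomisation replaces it, and amend 6.2 and 6.4.2.1 to match. Both routes are defensible, and greater power alone does not decide between them.
2. **Fix the denominator.** Analyse the binary service outcome in all randomised children by arm, with children who never reach the MDE or receive no service counted as not having the event. Report the eligible-only comparison as supportive.
3. **Use one marker.** Take the first service date as the sole marker of initiation and report the IFSP as an intermediate step.

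**Cost.** Wording in the SAP and, depending on the route, the protocol. The IFSP, service use and agency records are already planned, so the initiation route needs no new data. The completion route needs confirmation that completed or terminated status is actually recorded. If completion is replaced, the change to a named secondary outcome must be declared.

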## 6.3 Control of Bias and Confounding

Randomization and allocation concealment are the primary means of avoiding bias. Analytic strategies will also be used to control for residual confounding: (1) Stratification will control for imbalance not controlled by design. (2) Additional potential confounders will be evaluated for any residual association with treatment and included in model as needed. (3) Post randomization effects: The primary source of bias will arise after randomization from dropout and loss to follow-up. To address this problem and avoid missing data, we shall implement the following measures: (a) incentives to each family to complete the study, (b) collection of multiple contact numbers and tracking of changes, and (c) contact all randomized participants, even if they do not continue with their clinical contacts. Baseline data collection will include questions about factors that predict potential dropout, such as current living situations and regularity of contact with health care providers. (4) Our analytic model for treatment effect will include not only potential confounders but also predictors of dropout, to be able to relax assumptions about the missing data process. (5) To investigate the possibly informative dropout (for reasons related to the intervention), we will implement sensitivity analyses (6) For missing values in any of the outcome measurement tools, we will implement formal methods of multiple imputation. (7) We shall account for all dropouts and check all baseline information in real time for both invalid values and missing items and then prompt the child's caregiver for any corrections or clarifications. Then, if any covariates remain missing, we shall implement multiple imputation. (8) Attenuation bias from non-compliance might also occur if the child remains

in the study but fails to adhere to all aspects of the intervention. To address this potential problem, and to estimate the effect of treatment in the presence of full compliance, we will implement the methods outlined by Small and colleagues and by Nagelkerke. However, the “as randomized” approach will remain the primary method for assessing statistical significance of the intervention.

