## 5 STUDY EVALUATIONS AND MEASUREMENTS

### 5.1 Screening and Monitoring Evaluations and Measurements

#### 5.1.1 Medical Record Review

- Date of birth, Chart Review, History, Demographics
- Gestational age, sex, problem list, developmental assessments

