#### 5.1.2 Other Evaluations, Measures

##### 5.1.2.1 Main RCT

Following written informed consent, participant families will complete a baseline visit. Measures of demographic and biological variables (child age, sex, race/ethnicity, family income, maternal education level, and family structure), parental health literacy, and the home environment will be collected by research staff blinded to randomization assignment at this visit (Table 3). The Short Assessment of Health Literacy (SAHL, Appendix 3) is a validated 18-item measure of health literacy in both English and Spanish. The SAHL has good reliability ( $\alpha=0.80$  and 0.89) in Spanish- and English-speaking samples, and correlated well with other measures of health literacy including the REALM ( $r=0.94$ ,  $p<0.05$ ) and TOFHLA ( $r=0.68$ ,  $p<0.05$ ). SAHL scores  $\leq 14$  have been used to categorize low health literacy. The StimQ (Appendix 4) is a validated parent self-report questionnaire designed to measure cognitive stimulation provided in the home for children ages 5 to 72 months of age. The StimQ contains 4 subscales (availability of learning materials, reading, parental involvement in developmental advance, parental verbal responsiveness) and is available in English and Spanish. Internal consistency (Cronbach  $\alpha=0.88-0.93$ ) and test-retest reliability ( $ICC=0.93$ ) of the StimQ is excellent, and it correlates well ( $r=0.55$ ) with the IT-HOME Inventory, another measure of the home environment. Poverty will be assessed by

examining family income (<100% of the Federal Poverty Level) and maternal education status ( $\leq$  High School).

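### Protocol 6.3 promises dropout predictors in the treatment-effect model, but its two examples trace to no listed baseline measure and the SAP's Bayley analysis includes none

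*Protocol*

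**What the plan says.** Protocol Section 6.3 makes a two-step commitment. Item (3) says that baseline collection will ask about "factors that predict potential dropout, such as current living situations and regularity of contact with health care providers". Item (4) then uses the information: "Our analytic model for treatment effect will include not only potential confounders but also predictors of dropout". Its stated purpose is to weaken the assumptions about the missing-data process. Items (5) and (6) add sensitivity analyses for informative dropout and multiple imputation of missing outcome values. Section 6.4.2.1 also mentions multiple imputation as a way to handle differential loss.

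The data-collection sections list the baseline content. Section 3.1.1 has "Measures of demographic characteristics (child age, sex, race/ethnicity, family income, maternal education level, spoken language, and family structure) (Appendix 2"), plus health literacy (SAHL) and the home learning environment (StimQ). Section 5.1.2.1 has "Measures of demographic and biological variables (child age, sex, race/ethnicity, family income, maternal education level, and family structure"), again with health literacy and the home environment. Section 4.1.1 lists a medical record review, demographics, EI Engagement, StimQ and SAHL. The baseline column of Table 1 has demographics, SAHL, StimQ, poverty and EI Engagement. Section 5.1.1 gives the record review two bullets: a general one (date of birth, chart review, history, demographics) and "Gestational age, sex, problem list, developmental assessments".

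For Hypothesis 1c, the SAP compares Bayley cognitive and language scores by arm, controlling for sex, age and primary care site. It names no dropout predictor and no method for missing Bayley scores.

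**The concern.** The protocol expects dropout to be the main threat to the randomised comparison, and Section 6.5 expects it to differ by arm. Its answer is to measure what drives dropout and condition on it. If the SAP is followed as written, that step is lost. The Bayley comparison would then adjust for three variables that were presumably chosen because they are the stratification factors. Nothing in it would address families who leave because of unstable circumstances or weak contact with care. If children of such families also score lower, losing more of them from the control arm raises the control completers' mean relative to the intervention arm's and makes the intervention look less effective than it is.

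**Working it through.** **Step 1. Can the two examples be traced?**

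| Place | Living situation | Regularity of health-care contact |
|---|---|---|
| Table 1, baseline column | not named | not named |
| 3.1.1, itemised demographics | family structure only (partial overlap) | not named |
| 4.1.1, baseline procedures | not named | record review listed, content not given |
| 5.1.1, record review | not named | general chart review and history; no visit count |
| 5.1.2.1, itemised demographics | family structure only (partial overlap) | not named |

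Neither factor is named anywhere in these lists. This does not prove that the items are absent from the form. Section 3.1.1 refers to Appendix 2 for the demographics, and the appendix is not in the text reviewed. The prose lists are also not fully consistent: 3.1.1 includes spoken language and 5.1.2.1 does not.

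**Step 2. Are other candidate predictors collected?** Yes. Family income, maternal education, family structure, spoken language, SAHL, StimQ and baseline EI Engagement all appear in the lists above.

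**Step 3. Does the SAP use any of them for dropout?** No. The Aim 1 Bayley model has sex, age and site. StimQ, SAHL and income appear in the Aim 3 models, one at a time, to address moderation. They do not enter the Aim 1 comparison. The SAP's one rule for unavailable data concerns the discharge date in the duration of EI services, not the Bayley scores.

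**Step 4. How large is the exposure?**

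Inputs from the protocol: 360 randomised 1:1 (3.2), 300 with complete follow-up, control dropout double that of intervention, and a planned difference of 3 points (all 6.5). Assumptions: exactly 180 per arm, and a residual gap g (completers minus dropouts, after the modelled covariates) that is the same in both arms.

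- Lost in total: 360 - 300 = 60. Split 2:1, this is 40 control and 20 intervention.
- Loss rates: 40/180 = 22.2% and 20/180 = 11.1%.
- In an arm with loss L, the completer mean exceeds the full-arm mean by L x g. The completer difference is therefore biased by (L intervention - L control) x g = -0.111 x g.
- g = 3: -0.33 points. g = 5: -0.56. g = 8: -0.89.
- As a share of the planned 3 points: 0.33/3 = 11% to 0.89/3 = 30%.

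Section 6.5 also states about 130 control and 170 intervention completers. With 180 per arm, that is 50 and 10 lost (27.8% and 5.6%), a 5:1 ratio that does not match its own doubling rule. The figures above use the rule. The mismatch is a separate matter.

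**The case against.** A reader might infer that the promised dropout adjustment cannot be run at all. The documents do not support that. The two factors follow the words such as, so they are examples and not the required set. Item (4) asks only for predictors of dropout, and several plausible ones are collected. Section 6.3 is itself an instruction to collect the items, and the form that would settle the question is unseen. The general chart review and history in 5.1.1 could yield contact with care. It also cannot be said that staff who follow the schedule will lack these variables, because the schedule points to a form whose items are not visible.

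A reader might also take the bias figures as the cost of omitting these two items. They are not. The gap is assumed, no document gives a value for it, and nothing shows how much of it living situation or visit regularity would explain. The planned sensitivity analyses in item (5) would also bear on the same risk.

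Finally, the SAP does not withdraw Section 6.3, so one could hold that the protocol still governs.

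All of this narrows the point but does not remove it. The SAP gives an explicit covariate list for the Bayley comparison, and an analyst who works from it would omit both the dropout predictors and the imputation. The predictors are not specified in either document: 6.3 gives only two examples, neither traceable to a listed measure.

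**Conclusion.** The point holds as a failure to carry a commitment through. Section 6.3 items (3) and (4) are matched neither by a listed baseline measure for the two named examples nor by the SAP's Bayley analysis. The second half is the firmer one, because it rests on the SAP's own covariate list. The first half is a traceability gap that Appendix 2 might close.

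The exposure is about -0.3 to -0.9 points on a planned 3, for a completer comparison under the protocol's 2:1 dropout rule. It assumes 180 per arm and a common residual gap of 3 to 8 points. The range illustrates the risk in leaving dropout unaddressed and is not an estimate of what the omitted adjustment would recover. This is a worthwhile, low-cost improvement. It does not show that the planned analysis is impossible.

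**What to change.** 1. **SAP, Aim 1 Bayley analysis.** Name the dropout predictors, and enter them in the Bayley model and in the multiple-imputation model that Section 6.3 promises. Use those already collected: family income, maternal education, family structure, spoken language, SAHL, StimQ and baseline EI Engagement. Table 1 and 4.1.1 allow SAHL to be completed at a later visit, so state how late or missing SAHL values will be handled.
2. **Visit history.** Add kept and missed well-child visits before randomisation, extracted from the practice record where the record shows them. Section 9.5.1 already has records screened before contact. Limiting extraction to dates before randomisation keeps this a baseline covariate, and it can be done retrospectively for children already enrolled.
3. **Living situation.** If the demographics form holds such an item, use it and say so. If not, add a short item for children still to be enrolled, or amend 6.3 to name the variables that will actually be used. For children already enrolled without the item, amending 6.3 is the realistic course.
4. **Consistency.** Align Table 1 and Sections 4.1.1, 5.1.1 and 5.1.2.1 with the named predictors and their source (form item or chart field).

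The cost is minor chart-extraction time, at most one short baseline item, and wording changes in the two documents.
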